4.0 SUBJECT POPULATION and SELECTION CRITERIA

Patients presenting to urogynecology or gynecology clinic with vulvar symptoms and biopsy confirmed lichen sclerosis.

Inclusion criteria:

- Women
- Biopsy proven symptomatic vulvar lichen sclerosis
- Ability to understand the study, accept randomization and logistically follow-up with scheduled visits
- Post-menopausal

Exclusion criteria:

- Known vulvar malignancy
- Pregnancy or planning pregnancy or less than 3 months postpartum
- Current or prior diagnosis of any gynecologic malignancy
- Previous pelvic radiation therapy
- Allergy to topical steroid
- No active UTI, vulvar infection (candida, herpes, bacterial vaginosis, trichomoniasis or other infection)
- Pelvic organ prolapse > than Stage 2
- Treatment with systemic immunomodulators, topical calcineurin inhibitors (tacrolimus, pimecrolimus), or vulvar hormonal or vulvar topical steroid use within 2 months of enrollment
- History of vaginal mesh implant
- IUD (Intrauterine Device)
- Skindex-29 overall score <21, below mildly impaired health related quality of life threshold

5.0 SAMPLE SIZE CALCULATION

The study will consist of 2 study groups (LASER vs STEROID therapy). We expect improved subjective and objective results in the LASER group at 3 months post treatment or 6 months from enrollment compared with the STEROID group.

This study is designed as a two-group randomized clinical trial. Sample size calculations were conducted using the absolute change in the Skindex 29 as the primary end point. Our study will reach 80% power to detect a mean difference of 16 points on the Skindex 29 (sd=22 for both groups)²² between the study groups with 24 patients in each group, or 48 in total based on a one-sided two-sample t-test with alpha=0.05. By accounting for 10% attrition, we propose to recruit 52 patients to the study to be randomized with a 1:1 ratio to each group, with a blocked component for those who used topical clobetasol in the past. The Skindex-29 has validated cutoff categories for mildly, moderately, and severely impaired health related quality of life scores, the mean difference between each quality of life measure overall score is between 6 and 7. Therefore, powering the study for a detection of mean difference of 16 points should measure significant quality of life improvement.^{23,24}

Study Timeline:

	Intake Visit	Day 0	2 weeks	4 weeks-14 weeks	6 months	1 year
Vulvar biopsy (if never completed)	X					
Vaginal STEROID or LASER			STEROID daily x 4 weeks LASER monthly x 3 months	STEROID three times weekly x 8 more weeks, then as needed LASER STOP at 12 weeks		
Vaginal Health Index scale (VHIS)		X			X	x
SkIndex-29 Vulvar QoL Questionnaire Vulvovaginal Symptoms Questionnaire (VSQ)		X			X	x
Telephone call to check compliance and answer questions			X	X (8 weeks)		
Photodocumentation		X			X	x
Questionnaire of patient global impression of improvement and satisfaction PGI-I					X	x

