1.0 PURPOSE and OBJECTIVES

The purpose of this study is to compare the safety and efficacy of clobetasol propionate .05% ointment to fractional CO2 laser procedure for the treatment of vulvar lichen sclerosis.

Primary Outcome Measures:

- The primary outcome will be the subjective and objective cure of vulvar symptoms of itching, burning, dyspareunia at 12 weeks post treatment, or 6 months [Time Frame:12 weeks] using the SkinINDEX-29 and Vulvar Symptom Visual Analog Scale (VAS)

Secondary Outcome Measures:

- Complications [Time Frame: 6 week, 6 months, 1 year] pain, infection, de novo or worsening dyspareunia, contact dermatitis and burns
- Subjective Vulvovaginal Symptoms Questionnaire (VSQ)
- Objective Cure of Lichen Sclerosus [Time Frame:6 months, 1 year] using PHOTO documentation, Vulvar Signs Visual Analog Scale
- Health Related Quality of Life (HRQOL) based on patient global impression of improvement and satisfaction as well as the Vaginal Health Index [Time Frame: 6 months, 1 year]

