12.0 STATISTICAL ANALYSIS

Statistical intention-to-treat and per protocol analysis will be completed in R (version 3.4, Vienna, Austria 2017) with demographic and questionnaire scores reported as means and standard deviations or medians and interquartile ranges. Chi square or Fisher's exact, two-sample t-test and Mann Whitney U will be used to compare categorical, continuous, and non-parametric variables, respectively. D-Agostino test will be used to assess normality. Two-way ANOVA analysis of mean Skindex-29 score improvement based on prior steroid exposure and treatment group will be performed.

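### Section 5's 80% power holds for 48 completers and a one-sided 5% t-test, but 52 recruits less 10% leave 46–47, and Section 12 names no primary Skindex-29 test, side or alpha

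*Combined protocol and SAP*

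**What the plan says.** Section 5.0 (Sample Size Calculation) takes the change in Skindex-29 as the basis for sizing: "Sample size calculations were conducted using the absolute change in the Skindex 29 as the primary end point". It then states: "Our study will reach 80% power to detect a mean difference of 16 points on the Skindex 29", with an SD of 22 in both groups, "with 24 patients in each group, or 48 in total based on a one-sided two-sample t-test with alpha=0.05". The recruitment target follows: "By accounting for 10% attrition, we propose to recruit 52 patients to the study". Randomization is 1:1, "with a blocked component for those who used topical clobetasol in the past".

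Section 12.0 (Statistical Analysis) plans intention-to-treat and per protocol analyses. It assigns tests by type of variable: Chi square or Fisher's exact, then "two-sample t-test and Mann Whitney U will be used to compare categorical, continuous, and non-parametric variables, respectively". Its only sentence that names the Skindex-29 is: "Two-way ANOVA analysis of mean Skindex-29 score improvement based on prior steroid exposure and treatment group will be performed". Section 12 gives no alpha, no side and no confidence interval, and it does not say which test is primary.

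Section 1.0 states a purpose without direction: "The purpose of this study is to compare the safety and efficacy of clobetasol propionate .05% ointment to fractional CO2 laser procedure". Section 5.0, by contrast, says that a better result is expected with laser.

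**The concern.** A stated power belongs to one test, one side, one alpha and one number of analysed patients. Section 5 fixes all four. Two of its links to the rest of the plan then fail.

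- **Number analysed.** The 80% is for 48 completers, and the recruitment target does not deliver 48 at the attrition rate the plan itself assumes.
- **Test.** The one-sided basis appears only in Section 5. An analyst working from Section 12 could run a one-sided t-test, a two-sided t-test or the ANOVA F test, which has no direction, and each would be consistent with that section.

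The choice of side moves power by about 11 points, and for a band of plausible results it decides whether the trial is positive. If it is still open when data are seen, the conclusion may depend on a decision made afterwards.

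A smaller mismatch bears on the model. The blocking factor is past use of topical clobetasol, whereas the ANOVA factor is worded as prior steroid exposure. A woman who had used only another topical steroid could be classified differently under the two.

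**Working it through.** **Inputs, all from Section 5.0:** difference 16; SD 22 in each group; alpha 0.05, one-sided; 24 per group; 52 recruited; 10% attrition.

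**Method.** SE = 22 × √(1/n₁ + 1/n₂). Noncentrality = 16/SE. Power comes from the noncentral t distribution with n₁ + n₂ − 2 degrees of freedom.

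**1. The plan's own figure.** With 24 + 24, SE = 22 × √(2/24) = 6.351 and noncentrality = 16/6.351 = 2.519. One-sided 5% power is 79.9%. The stated 80% is reproduced.

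**2. Attrition.** 52 × 0.9 = 46.8, so 46–47 completers. Keeping 48 after a 10% loss needs 48/0.9 = 53.3 recruits. With 52 recruited, 48 remain only if attrition is at most (52 − 48)/52 = 7.7%, or 4 patients.

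**3. Power by completers and side (t-test).**

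| Completers | SE | One-sided 5% | Two-sided 5% |
|---|---|---|---|
| 48 (24 + 24) | 6.351 | 79.9% | 69.4% |
| 47 (24 + 23) | 6.420 | 79.1% | 68.4% |
| 46 (23 + 23) | 6.487 | 78.3% | 67.4% |

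Attrition costs 1–2 points. The side costs about 11.

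**4. Difference detectable with 80% power.** At 47 and 46 completers this is 16.2 and 16.4 points one-sided, and 18.4 and 18.6 points two-sided.

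**5. The two-way model.** The F test for treatment has one numerator degree of freedom and is equivalent to a two-sided t-test. Take an additive model (treatment plus prior exposure; N − 3 error degrees of freedom) and assume that prior exposure explains no variance, so that the residual SD stays at 22. F-test power is then 69.3%, 68.4% and 67.4% at 48, 47 and 46 completers. A one-sided test of the treatment effect in the same model gives 79.9%, 79.1% and 78.3%. The loss therefore comes from the default test and not from the model.

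**6. Sensitivity to that assumption.** The documents do not say how much variance prior exposure explains. If the share is R², the residual SD is 22 × √(1 − R²). F-test power is then:

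| R² (assumed) | 46–47 completers |
|---|---|
| 0 | 67–68% |
| 0.10 | 72–73% |
| 0.20 | 77–78% |
| 0.25 | about 80% |

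**7. Results for which the side decides.** The smallest significant observed difference is SE × t. With SD 22:

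- 47 completers (45 df): one-sided 6.420 × 1.679 = 10.78; two-sided 6.420 × 2.014 = 12.93.
- 46 completers (44 df): one-sided 6.487 × 1.680 = 10.90; two-sided 6.487 × 2.015 = 13.07.

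At either number, an observed laser advantage between about 10.9 and 12.9 points is significant one-sided but not two-sided.

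**The case against.** The best defence is that Section 5 already states test, side and alpha, with a directional expectation. Section 12 assigns the two-sample t-test to continuous variables, and the change in Skindex-29 is one. On that reading the sizing test is present in the analysis section, and the ANOVA is a supplementary look at prior exposure. This is a fair reading, and nothing in the plan calls the ANOVA primary. But nothing calls the t-test primary either, and its side and alpha are not repeated. The defence narrows the point to that omission and does not remove it.

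A reader might go further and infer that the trial really has only 67–69% power. The documents do not support this. The figure applies only if a two-sided or F test turns out to be primary, and for the F test it also needs prior exposure to explain no variance.

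A reader might also infer that the attrition slip overturns the 80%. It does not, because 78–79% is within 2 points. Nor do the documents show that a one-sided test is wrong here: the neutral purpose in Section 1 and the directional expectation in Section 5 point different ways.

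Finally, Section 12 does report questionnaire scores as means and SDs or medians and interquartile ranges, so a result favouring steroid would be visible. What is missing is a planned interval for the difference.

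**Conclusion.** The point holds in a limited form and should be fixed. The sample-size arithmetic in Section 5 is right for the case it describes. Two links are missing.

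- **Completers.** The plan's own attrition leaves 46–47, so one-sided power is 78–79%. This is minor and would not justify a change by itself.
- **Primary test.** Section 12 does not fix the test, side or alpha. If a two-sided or F test is used, power for 16 points is about 69% at 48 completers and 67–68% at 46–47.

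These figures rest on the plan's 16 points and SD 22, on treating attrition as loss of the primary outcome (Section 12 gives no method for missing data) and, for the F test, on prior exposure explaining no variance. It would have to explain about 25% for the F test to reach 80% at 46–47 completers.

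**What to change.** **Section 5.** Keep 52. Restate expected completers as 46–47 and one-sided 5% power for 16 points as 78–79%. Beside it give the two-sided 5% figures: 67–68% power, and 18.4–18.6 points detectable with 80% power.

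**Section 12.**

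- Name one primary test of absolute change in Skindex-29, with side and alpha matching the power stated in Section 5.
- Preferably, use the treatment effect from an additive model with treatment and the blocking factor, defined as in Section 5 (past topical clobetasol use). Test the interaction separately.
- Report a two-sided 95% confidence interval for laser minus steroid, whichever side is chosen.

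The side is the sponsor's choice, to be fixed before data are seen. If one-sided 5% is kept, Section 12 should say so and give the reason.

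**Cost.** Wording only, with no added patients. Including the blocking factor costs one error degree of freedom, under 0.1 point of power. The stated power becomes less favourable: slightly so (78–79%) if one-sided is kept, and 67–68% if two-sided is chosen. For information, a two-sided t-test reaches 80% at 31 per arm, that is 62 completers, or 62/0.9 = 68.9, so 69 recruited (70 for equal arms). The fix does not ask for that increase.

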2.0 BACKGROUND and SIGNIFICANCE

Vulvar lichen sclerosis (LS) is a well-characterized dermatosis resulting in labial atrophy, synechiae and introital narrowing and can often cause dyspareunia, itching and co-existent vulvar pain. Biopsy is necessary to confirm the clinical diagnosis and the mainstay of treatment usually consists of topical steroid therapy.¹

Clobetasol propionate and mometasone furoate are potent topical steroids that have long been considered gold-standard treatment for vulvar lichen sclerosis and work through anti-inflammatory, anti-mitotic, and immunosuppressive effects. One of the complications of long-term steroid use, however, is potential thinning of the vulvar skin, therefore limiting long-term use. Other therapeutic options include topical calcineurin inhibitors, surgery including incision and skin graft treatment, cryotherapy and phototherapy. Table 1 summarizes current clinical comparative trials for lichen sclerosis involving topical steroid therapy. Clobetasol propionate has a range of efficacy from 61-91% depending on the selected outcome criteria.

Table 1.

Author/year	Study Design	N	Outcome	Results
Bracco, GL 1993 ²	RCT Clobetasol vs. testosterone vs. progesterone vs. cream based therapy	79	-Subjective scaled symptom remission of vulval LS -Objective histologic and gross improvement	-75% remission with Temovate versus 10% Progesterone, 20%Testosterone, and 10% cream based treatments had subjective remission of LS -Only Clobetasol propionate had significant histologic and gross improvement.
Terra S, 2014 ³	RCT clobetasol vs. phototherapy	15	-Mean relative reduction of total clinician's score (TCS): subjective pruritus and burning/pain VAS, Skindex-2, 20 MHz- ultrasonography, histopathological analysis	35.6% decrease in mean (total clinical score) TCS in UV-A1 phototherapy group -51.4% decrease in mean TCS for clobetasol propionate group; Skindex-29, pruritus, burning/pain significantly decreased -Phototherapy group's only significant difference was with burning/pain -Significant difference in dermal density on ultrasound and histopathological reduction of

				inflammatory infiltrate in clobetasol propionate group and not Phototherapy group

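### The sample size assumes an unjustified one-sided 5% test in favour of laser, and the analysis section states neither sidedness nor alpha, so either the error rate or the stated power is not what a reader would assume

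*Combined protocol and SAP*

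**What the plan says.** Section 1.0 gives the aim without a direction: to "compare the safety and efficacy of clobetasol propionate .05% ointment to fractional CO2 laser procedure". Section 2.0 describes clobetasol and mometasone as "potent topical steroids that have long been considered gold-standard treatment for vulvar lichen sclerosis".

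Section 5.0 introduces a direction: "We expect improved subjective and objective results in the LASER group at 3 months post treatment or 6 months from enrollment", compared with steroid. It then sizes the trial on Skindex-29: "Sample size calculations were conducted using the absolute change in the Skindex 29 as the primary end point". The inputs are a 16-point difference, an SD of 22 in both groups, 80% power and 24 per group, "based on a one-sided two-sample t-test with alpha=0.05". No reason is offered for the one-sided test, and no non-inferiority margin appears anywhere.

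Section 12.0 says that chi-square or Fisher's exact, "two-sample t-test and Mann Whitney U will be used to compare" the groups according to variable type, and adds a two-way ANOVA of Skindex-29 improvement by prior steroid exposure and treatment group. It gives no sidedness and no significance level. The only alpha in the document is the one in Section 5.0.

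**The concern.** A one-sided test is directional: it can return laser better, or not shown. The question in Section 1.0 has a third possible answer, that the established steroid is better. Section 2.0 reports clobetasol efficacy of 61-91% and describes the earlier CO2 laser studies in lichen sclerosus as small and retrospective, so that third answer is plausible. Expecting laser to win is not by itself a reason to leave it out.

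Two things are at stake. One is the error rate for a claim that a new device beats standard treatment. The other is whether the advertised 80% power is real. Because Section 12.0 does not settle sidedness, the choice could be made after the data are seen. For an observed laser advantage between 10.7 and 12.8 points, that choice alone decides whether the result is significant.

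**Working it through.** **Inputs, all from Section 5.0:** difference 16 points, SD 22 in each group, 24 per group, alpha 0.05 one-sided, power 80%, 10% attrition, 52 recruited. The tested direction (laser better) is inferred from the expectation stated in the same section.

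**1. Reproduce the plan's figure.** Normal approximation, n per group = 2 × (z_alpha + z_power)² × SD² / difference².
- One-sided 5%: 2 × (1.645 + 0.842)² × 22² / 16² = 23.4, so 24 per group and 48 in total. This matches the plan.
- Power at 24 per group: 80.9% (normal) or 79.9% (noncentral t, 46 df).

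**2. The same inputs, two-sided 5%.**
- 2 × (1.960 + 0.842)² × 22² / 16² = 29.7, so 30 per group (60 evaluable). The noncentral t gives 31 per group (62 evaluable).
- The stated 48 therefore follows from the one-sided 5% test and not from a two-sided one.

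**3. If the analysis is one-sided, as sized.**
- Standard error of the difference: 22 × √(2/24) = 6.35 points.
- Smallest observed difference that is significant: one-sided 5%, 1.679 × 6.35 = 10.7 points; two-sided 5%, 2.013 × 6.35 = 12.8 points.
- Chance of declaring laser better when the arms are equal: 5%, against 0.05 / 2 = 2.5% for the two-sided test.
- Example: an observed laser advantage of 12 points gives t = 12 / 6.35 = 1.89, so p = 0.033 one-sided and 0.065 two-sided.
- An observed steroid advantage of any size is reported as not significant.

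**4. If the analysis is two-sided at 5%.**
- Noncentrality: 16 / 6.35 = 2.52. Power at 24 per group: 69.4% (noncentral t) or 71.2% (normal), against the stated 80%.
- Difference detectable with 80% power at 24 per group: about 18.2 points, against about 16.0 one-sided.
- By symmetry, a true 16-point steroid advantage would also be detected with about 69% power.

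**5. Size needed to keep 80% power for 16 points, two-sided.** 60 to 62 evaluable. With 10% attrition, 60 / 0.9 = 66.7 and 62 / 0.9 = 68.9, so 67 to 69 recruited, or 68 to 70 for equal arms, against 52 planned.

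**The case against.** The strongest reply is that Section 5.0 explains how a number was obtained, while Section 12.0 governs the analysis, and Section 12.0 does not say one-sided. The only analysis there that names Skindex-29 is the two-way ANOVA. The F-test for a two-level treatment factor is ordinarily non-directional and can reject in favour of steroid. This stands. A reader might infer from Section 5.0 that the trial cannot conclude that steroid is better and carries twice the usual false-positive risk for laser. The documents do not support that as a flat statement: both consequences hold only if the final analysis is run as sized.

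A reader might also infer that a steroid advantage would be hidden. It would not. Section 12.0 commits to reporting questionnaire scores by means and SDs or medians and interquartile ranges, so the size and direction would be visible. Only the formal claim would be lost.

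It can also be said that a pre-specified one-sided test is a valid design for a directional hypothesis, that it controls its error at the stated 5%, and that 2.5% per side is a convention to which the plan never commits. That is true. But Section 5.0 gives an expectation and no justification, and Section 1.0 states the aim without a direction.

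None of this removes the problem. If the ANOVA or a two-sided t-test is what will be run, the power statement in Section 5.0 does not describe it.

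**Conclusion.** The point holds in conditional form. The sample size rests on a one-sided 5% test that is not justified and does not match the open question in Section 1.0, and Section 12.0 leaves sidedness and alpha unstated. A defect remains on either reading:

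- **Analysed one-sided at 5%:** the false-positive risk for laser is 5% rather than 2.5%, the bar is about 2.1 points lower (12.8 − 10.7), and steroid superiority cannot be formally declared.
- **Analysed two-sided at 5%:** power for 16 points is about 69% (71% by normal approximation), roughly 10 points below the 80% stated.

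The figures assume the plan's SD of 22, 24 evaluable patients per group and a two-sample t-test. The power of the ANOVA would differ somewhat, depending on how much variance prior steroid exposure explains, which the documents do not give. The one-sided 5% calculation itself is reproduced; the fault is not in its arithmetic.

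**What to change.** In Sections 5.0 and 12.0, state that laser and steroid are compared on Skindex-29 change with a two-sided 5% test and a two-sided 95% confidence interval for the difference, and that a conclusion is allowed in either direction. Keep the planned sample size and restate its power beside it: about 69% for 16 points, or 80% for about 18.2 points, with 24 per group.

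This is protocol and SAP wording, with no extra patients or data. Its cost is a less favourable stated power. Keeping 80% power for 16 points would instead need about 60 to 62 evaluable patients; that is the sponsor's option and not part of this change. The rule should be fixed before outcome data are compared by arm, since Section 8.0 plans an analysis of ongoing data at half recruitment.

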6.0 DATA COLLECTION and TRANSMISSION

The data will be collected from study participants at MedStar Washington Hospital Center or other Medstar Urogynecologic Clinic. All data collection will be performed by research staff. The baseline, 6 month, and 1 year visits will be in-person and include clinic evaluations. The 2 week and 2-month telephone call will be performed by the research coordinator. At screening, each subject will be assigned a subject identification. Case report forms will be generated for each subject and completed by the investigator or study coordinator. Original case report forms will be securely maintained. Data will be entered into a secure RedCAPS Database which provides complete auditing for data management processes.

De-identified backup data will be kept in locked files at the participating site. Plans for publication will be handled by the investigators at MedStar Washington Hospital Center and will adhere to publication policies.

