7.0 HUMAN SUBJECT RESEARCH and ETHICAL CONCERNS

Signed consent in English will be obtained from each participant / patient at the time of enrollment. The objectives of the study and the data collection procedures will explained to every prospective participant before study enrollment. An IRB-approved consent document will be used for protocols. Consent for the patients includes the right of the subject:

- To either withdraw or refuse participation without prejudice at any time during the study;
- To voluntarily participate in the research;

- To receive new information about the study as it becomes available;
- To understand the procedures, risks, and benefits;
- To maintain confidentiality of personal medical information.

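### A woman who does not return for the in-person 6-month visit has no primary-endpoint value, and with no missing-data method the intention-to-treat comparison is complete-case by default

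*Combined protocol and SAP*

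**What the plan says.** Section 5.0 fixes the endpoint behind the sample size: "Sample size calculations were conducted using the absolute change in the Skindex 29 as the primary end point". A change score needs a baseline and a follow-up value from the same woman.

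The timeline in Section 5.0 places Skindex-29 and VSQ at Day 0, 6 months and 1 year. Section 3.0 gives the same pattern for all the questionnaires, including the symptom VAS, and ties the investigator-rated signs to those times. The first post-baseline point is 12 weeks after treatment or 6 months from intake. On how the data are obtained, Section 6.0 says: "The baseline, 6 month, and 1 year visits will be in-person and include clinic evaluations". The calls at 2 and 8 weeks are for adherence and queries; no efficacy instrument is attached to them. Neither remote completion nor an assessment at early exit is described.

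On loss, Section 5.0 says: "By accounting for 10% attrition, we propose to recruit 52 patients". On analysis, Section 12.0 says: "Statistical intention-to-treat and per protocol analysis will be completed in R". It defines neither analysis set, gives no missing-data method, and lists t-tests, Mann-Whitney tests and a two-way ANOVA of Skindex-29 improvement. The only exit the protocol mentions is the consent right in Section 7.0: "To either withdraw or refuse participation without prejudice at any time during the study".

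**The concern.** A change score with no follow-up value falls out of every test listed in Section 12.0. For a woman who does not come back by 6 months, the trial holds a baseline score and no later efficacy score at the primary time point. Unless the plan says otherwise, the analysis labelled intention-to-treat contains only those who returned.

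That matters more here than in a blinded trial. Patients know their treatment (Section 3.0), and the burdens differ: three clinic laser sessions, with pain, blistering and burns among the listed risks (Section 8.0), against an ointment. Loss related to both arm and outcome is plausible. If women who did badly on one arm leave more often, that arm's completers look better than the arm as randomised. If it is the laser arm, the error favours the hypothesis tested one-sided.

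An analysis rule written later cannot recover scores that were never taken. Yet the endpoint that sizes the trial is a self-completed form (Appendix 2), which does not need a clinic visit.

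**Working it through.** **Inputs from Section 5.0.** Difference and power: "Our study will reach 80% power to detect a mean difference of 16 points on the Skindex 29". Spread: "sd=22 for both groups". Size and test: "with 24 patients in each group, or 48 in total based on a one-sided two-sample t-test with alpha=0.05". Recruitment is 52 at 1:1, so 26 per arm, with 10% attrition.

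**1. The plan's own figure.** n per arm = 2(z₀.₉₅ + z₀.₈₀)² × SD²/Δ² = 2 × (1.645 + 0.842)² × 22²/16² ≈ 23.4, rounded up to 24. Exact t-test power at 24 per arm is 0.799. The stated figure reproduces.

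**2. Expected loss.** 0.10 × 52 = 5.2, about 5 women, leaving 46.8 (23.4 per arm).

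**3. Effect on power.** Exact one-sided power is 0.83 with 26 per arm and about 0.79 with 23.4 per arm. Power is hardly affected, so the issue is bias.

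**4. Bias of a complete-case comparison.** Suppose k of the 26 women in an arm are lost and their mean change would have been g points worse than that of the arm's completers. The mean over all 26 is the completers' mean minus (k/26) × g, so the completers' mean is too favourable by (k/26) × g. The bias in the difference between arms is (k₁ − k₂)/26 × g.

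The documents give neither the split of losses nor g. With 5 losses, and g assumed at 8, 16 (the design difference) or 22 (the SD):

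| Losses by arm | g = 8 | g = 16 | g = 22 |
|---|---|---|---|
| 3 v 2 | 0.31 | 0.62 | 0.85 |
| 4 v 1 | 0.92 | 1.85 | 2.54 |
| 5 v 0 | 1.54 | 3.08 | 4.23 |

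At g = 16 the range is 0.62/16 = 4% to 3.08/16 = 19% of the target difference. Equal losses with equal g would cancel.

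**5. Scale.** The standard error of the difference at 24 per arm is 22 × √(2/24) = 6.35 points, so 3.08 points is 3.08/6.35 = 0.48 of a standard error.

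**6. What recovery is worth.** At g = 16, each woman recovered in the 5-versus-0 case removes 16/26 = 0.62 points of bias.

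**The case against.** The strongest reply is that the plan already limits loss. Section 4.0 admits only women able to keep the scheduled visits, both arms receive two calls, and attrition is budgeted. That stands as mitigation, but the plan still expects about 5 women to be lost and says nothing about how they enter the analysis.

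Several stronger readings are tempting, and the documents do not support them:

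- *That nothing is collected before 6 months.* Section 1.0 lists complications as a secondary outcome at 6 weeks, and Section 8.0 promises adverse-event monitoring. The gap concerns efficacy measures. The timeline shows no 6-week contact, and those two sections should be reconciled.
- *That every woman who stops treatment is lost.* No text ends follow-up when laser or steroid stops, and questionnaires are set by time. The Section 7.0 line is a consent right, not a discontinuation rule. The plan is silent on this.
- *That the visit schedule alone makes the analysis completers-only.* It takes the schedule together with the silence of Section 12.0.
- *That a missed 6-month visit removes a woman altogether.* She may still give a 1-year score, though not at the primary time point.
- *That 3.1 points is the expected bias.* It needs all five losses in one arm and an assumed 16-point gap.
- *That the bias could not be examined at all.* Baseline scores and losses per arm allow bounding, though they cannot show what the missing scores were.

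**Conclusion.** The point holds in this form: no efficacy measure is scheduled between Day 0 and 6 months, the 6-month visit is in person with no remote route described, and no missing-data method is given. Women who do not return by then have no primary-endpoint value, and intention-to-treat is complete-case by default.

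With the plan's 10% attrition and an assumed 16-point deficit in those lost, the bias is about 0.6 to 3.1 points against a 16-point target. The upper end is about half a standard error. This would not by itself overturn a 16-point effect, but it could matter to a borderline result. Attrition above 10% would allow more bias. The change is worth making because it is cheap and recovers primary-endpoint data that cannot be reconstructed afterwards.

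**What to change.** **Section 6.0.** Keep the in-person visit as the default at 6 months and 1 year. Let a woman who will not attend complete Skindex-29, the symptom VAS, VSQ and PGI-I by mail, by telephone or through the existing REDCap database at the same time points, and record the mode. State that women who stop study treatment are still asked for these questionnaires unless they withdraw consent.

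**Section 12.0.** Define the intention-to-treat comparison as all randomised women with a 6-month score, however collected, analysed in the arm assigned. Report losses by arm. Add a sensitivity analysis that assigns a range of assumed values to those still missing, varied separately by arm, and shows where the conclusion would change.

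**Cost.** A short amendment, with no new visit or staff. The downside is a small mode difference in the few women who answer remotely, which the recorded mode lets the analyst examine. Investigator-rated signs, the Vaginal Health Index and photographs would still be missing for women who do not attend.

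Giving Skindex-29 at the existing 8-week call may look like a natural addition, but I would not include it. Eight weeks falls during treatment in both arms, the form's 4-week recall would cover the treatment period, and the score could not stand in for the 6-month endpoint. It would also be taken by telephone in every woman, not just a few.
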